##### **5.2 Secondary Clinical Endpoints**

The following secondary clinical endpoints will be assessed:

###### **5.2.1 Morbidity/Mortality**

- Neurologic morbidity measured at 24-hours post-procedure. Morbidity is defined by neurologic worsening measured by a greater than or equal to 4-point change in the NIH Stroke Scale (NIHSS) from pre-surgical baseline.

- Mortality through end of study follow-up (12 to 18 month visit)

### 5.2.2 Clinical Outcome

- Modified Rankin Scale score at the 3 to 6 month and 12 to 18 month visits. The Modified Rankin Scale ranges from 0 (no symptoms) to 6 (dead) (Broderick 2017)

Scale Score	Clinical Outcome
0	No symptoms
1	No significant disability. Able to carry out all usual activities, despite some symptoms
2	Slight disability. Able to look after own affairs without assistance, but unable to carry out all previous activities
3	Moderate disability. Requires some help, but able to walk unassisted
4	Moderately severe disability. Unable to attend to own bodily needs without assistance, and unable to walk unassisted
5	Severe disability. Requires constant nursing care and attention, bedridden, incontinent.
6	Dead

### 5.2.3 Re-hemorrhage/Re-treatment

- Incidence of re-hemorrhage through the end of study follow-up at the 12 to 18 month visit.
- Incidence of re-treatment of the aneurysm through the end of study follow-up at the 12 to 18 month visit.

### 5.2.4 Packing Density

- Volumetric filling of the aneurysm, reported as a percentage and calculated using AngioCalc ([www.angiocalc.com](http://www.angiocalc.com)).

## 5.3 Secondary Safety Endpoints

The following secondary safety endpoints will be assessed:

### 5.3.1 Serious Adverse Events

- Incidence of SAEs through end of study follow-up

## 6. STATISTICAL METHODOLOGY

### 6.1 General Principles

Study day will be calculated from the reference start date and will be used to show the study days of assessments and events. Reference start date is defined as the date of randomization unless otherwise specified.

Continuous variables will be summarized using the following descriptive statistics: number of non-missing values, means, standard deviations, medians, interquartile range, maximum, and minimum. Categorical variables will be summarized using number of non-missing values, counts, and percentages.

Rates of events will be calculated as the ratio of the total number of events recorded divided by the total patient-time. Total patient-time will be calculated by summing the time (in study time units, e.g., days or months) that patients were at risk for a specific event from the reference time point until either study exit or the end of the time period of interest. Rates and their 95% confidence intervals will be reported. Time-to-event variables will be summarized using the Kaplan-Meier method or, in the presence of competing risk, by cumulative incidence curves accounting for competing events as appropriate.

In the situation where an event date is partial or missing, study day, and any corresponding durations are to appear partial or missing in listings. If a partial event date is recorded (i.e. the month and year are known but not the day) and is necessary to calculate patient-time at risk or patient-time to the event, the missing event day will be imputed to the 15th day of the known month and year.

For any variable measured at multiple points in time, change from baseline will be calculated as the difference between the value of the variable at a specific point in time (e.g. 1 year) minus the baseline value. Relative change from baseline will be calculated as the value of a parameter at a specific point in time minus the baseline value of the parameter divided by the baseline value of the parameter. Percent change will be calculated as the relative change multiplied by 100.

All hypothesis testing will be conducted at the 0.05 two-sided significance level unless otherwise specified. P-values will be rounded to three decimal places. P-values less than 0.001 will be reported as <0.001 in tables. P-values greater than 0.999 will be reported as >0.999.

Should any of the statistical methods proposed prove unsuitable during data analysis, more appropriate methods will be used. These include data transformation (for example to a logarithmic scale) to satisfy model assumptions such as normally distributed residuals with constant variance, the application of non-parametric techniques, or the use of a different link function or modeling technique. The SAP will be updated with the methods used and the justification for the change prior to data set and database lock.

Additional ad-hoc analyses may be conducted as deemed appropriate.

All analyses will be conducted using SAS V9.4 or higher and R V4.1.1 or higher.

## **6.2 Missing Data**

### **6.2.1 Missing Baseline Data**

Missing baseline values will not be imputed in summaries of baseline characteristics. Summaries will be based on all available data.

### **6.2.2 Missing Primary Outcome Data**

The plan for handling missing primary outcome data is outlined in section 6.5.3 below.

### **6.2.3 Missing Secondary Outcomes Data**

The plans for handling missing secondary outcome data are outlined by outcome in section 6.6 below.

## **6.3 Crossover and Missed Treatment**

Crossovers (patients who after randomization switch from the allocated treatment to the non-allocated

treatment) will be analyzed in the group they were randomized according to the ITT principle in all efficacy analyses. Safety analyses will be conducted according to section 4 above.

## 6.4 Patient Characteristics

### 6.4.1 Patient Disposition

Disposition will be summarized in the screened and ITT populations.

Disposition summaries of the screened population will include:

- The number of patients screened
- The number and percentage of eligible patients randomized

Disposition in the ITT population will be summarized by randomization group and will include:

- The number of patients randomized
- The number and percentage of patients who received their assigned treatment
- The number and percentage of patients withdrawn or lost to follow-up by the 3 to 6 month visit and the primary reason for withdrawals
- The number and percentage of patients withdrawn or lost to follow-up by the final study visit at 12 to 18 months and the primary reason for withdrawals

### 6.4.2 Protocol Deviations

Protocol deviations and violations are defined as deviations from the procedures outlined in the protocol. All statistical analyses and summaries will be conducted on an intent-to-treat basis with the exception of safety analyses, which will be conducted on the safety population.

### 6.4.3 Patient Characteristics

#### 6.4.3.1 Demographic characteristics

Demographics including age, gender, race, and ethnicity will be summarized by randomization assignment using the appropriate descriptive statistics.

#### 6.4.3.2 Baseline characteristics

Baseline characteristics will be summarized by randomization assignment using the appropriate descriptive statistics. The specific baseline variables collected include randomization stratification factors, anthropometrics (weight, height), medical history (prior aneurysms treated, smoking status, pre-existing conditions), presenting symptoms, Modified Rankin Scale score, and rupture characteristics (if ruptured, time since rupture at randomization, Fisher Scale, Hunt and Hess scale, WFNS grade, IVH presence, ICH presence, and presence of infarct prior to embolization).

#### 6.4.3.3 Operative characteristics

Operative data including aneurysm characteristics (height, width, depth, neck size, shape, type, and location), heparin dosing, activated clotting time (ACT), medications, presence of vasospasm, and coil/device log data will be summarized by randomization assignment using the appropriate descriptive statistics.

### 6.5.2 *Determination of Sample Size*

Sample size calculations were based on the primary endpoint under the following assumptions and operating characteristics: a) 73% angiographic occlusion at the 12-18 month visit in patients receiving smaller coils (control arm); b) a 9% absolute improvement (to 82%) in the incidence of angiographic occlusion in patients receiving larger coils; c) Approximately 80% power on a two-sided proportion test; and d) a significance level of 0.05. A sample size of 650 (325 in each arm) will allow us to detect the specified effect size with adequate power. Sample size was calculated using the `power.prop.test` function in R (R Core Team 2021).

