## **4.2 Exclusion Criteria**

1. Patient has more than one aneurysm requiring treatment in the current treatment session, and only one of those to-be treated aneurysms fits the FEAT inclusion criteria (i.e., - if either (1) a patient has multiple aneurysms, but only one will be treated at enrollment; or (2) if two or more aneurysms are treated during the current treatment session and BOTH are able to be enrolled, then they remain eligible for the trial. Non-treated additional aneurysms may be treated at a later date with any coil type that the operator chooses).
2. Target aneurysm has had previous coil treatment or has been surgically clipped.
3. Hunt and Hess score is 4 or 5 after subarachnoid hemorrhage.
4. Inability to obtain informed consent.
5. Medical or surgical co-morbidity such that the patient's life expectancy is less than 2 years.

Death or procedural/disease-related morbidity may result in some subjects not having follow-up angiography. For the primary outcome of angiographic recurrence, the analysis will be conducted 2 ways: (1) among only those patients with angiographic assessment at 12-18 months, and (2) among patients with angiographic assessment, plus those with death or procedural/disease-related morbidity that precluded angiography, with such patients counted as incident events. Similarly, for the secondary outcome of treatment-related morbidity and mortality, patients without angiographic evaluation due to death or procedural/disease-related morbidity will be counted as incident events in the analysis.

Use of coil-assist devices (stent, balloon, etc.) will be allowed. Intention to use such a device will be recorded pre-procedure, along with dome to neck ratio and rupture status.

Additional critical components of the study design include the large number of patients required to demonstrate a statistically significant difference, and the subsequent significant length of time required to allow enrollment. Therefore, we propose a three phase study design to address the following concerns:

- 1) A 6-year time window renders any conclusions irrelevant due to progress in technology. Typically the conclusions of long-term studies in the endovascular space are called into question because they do not include technology that is considered modern by the time the study is completed. Stryker has multiple coil iterations planned over the next 5 years. To not involve these new technologies would make the study non-viable to

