## **9. Statistical Methods**

### ***9.1 Sample Size Estimate and Power of the Study***

Based upon a presumed absolute improvement in recanalization rate (defined as an increase in Raymond Scale from immediate to 12-18 month follow-up, as determined by the core laboratory analysis) of 9% (73% recanalization rate for non-Eighteen versus 82% for Eighteen) with an Alpha 0.05 and Power = 80, 325 patients would be required for each arm (at least 650 total patients).

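### 325 per arm gives 78.6% power with complete outcomes rather than the protocol's 80%, and neither sample-size section allows for missing 12–18 month angiograms

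*Combined protocol and SAP*

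**What the plan says.** SAP 6.5.2 takes 73% occlusion at 12–18 months in the smaller-coil arm and "a 9% absolute improvement (to 82%) in the incidence of angiographic occlusion in patients receiving larger coils". It claims "Approximately 80% power on a two-sided proportion test" at a significance level of 0.05, names R's `power.prop.test`, and concludes that "A sample size of 650 (325 in each arm) will allow us to detect the specified effect size with adequate power".

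Protocol 9.1 uses the same two percentages and the same 325, but says that "with an Alpha 0.05 and Power = 80, 325 patients would be required for each arm", with a total of at least 650. It does not say approximately, and it names neither a function nor sidedness. It describes the percentages as "73% recanalization rate for non-Eighteen versus 82% for Eighteen", having just defined recanalization as an increase in Raymond Scale from immediate to 12–18 month follow-up.

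Neither section mentions missing outcomes. Other sections do:

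- Protocol 4.2: "Death or procedural/disease-related morbidity may result in some subjects not having follow-up angiography".
- SAP 6.5.3 sets rules for missed angiograms, angiograms the core lab cannot read, and deaths.
- SAP 6.4.1 will tabulate withdrawals and losses to follow-up.

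**The concern.** A sample-size statement that gives both rates, the alpha, the sidedness and the software function should reproduce. The protocol's version does not, and the gap is on the unfavourable side. More importantly, 650 is used both as the number randomized and, implicitly, as the number with an observed primary endpoint. Delivered power equals the calculated figure only if every 12–18 month outcome is obtained.

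What is at stake is how the primary result is read. Under SAP 6.8, a primary p-value of 0.05 or more stops the testing hierarchy with a conclusion of no treatment effect, and the other four hypotheses are not formally tested. A reader judging such a result will look at the stated power, so it should be accurate and should say what it assumes. The label in protocol 9.1 adds a second difficulty: taken literally, it makes the larger-coil arm the worse one.

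**Working it through.** **Inputs.** p1 = 0.73, p2 = 0.82, difference 0.09, two-sided alpha 0.05, 325 per arm (SAP 6.5.2; two-sidedness also in SAP 6.1); 1:1 allocation (SAP 3.1). The mean rate is 0.775.

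**Step 1: sample size for 80% power.** `power.prop.test` uses a pooled variance under the null and no continuity correction:

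n = [1.96·√(2·0.775·0.225) + 0.8416·√(0.73·0.27 + 0.82·0.18)]² / 0.09²

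- First term: 1.96·√0.34875 = 1.1575
- Second term: 0.8416·√0.3447 = 0.4941
- n = (1.6516)² / 0.0081 = 336.8, so 337 per arm (674 in total)

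Running the function in R returns 336.76. Other conventions give 335 (unpooled), 335 (arcsine), 359 (continuity-corrected) and 266 (one-sided). None gives 325. The pooled formula gives 325 when the target is 78.5% power.

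**Step 2: power at the planned size.** Power = Φ[(0.09·√n − 1.1575) / √0.3447].

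At n = 325: (1.6225 − 1.1575) / 0.5871 = 0.792, and Φ(0.792) = 78.6%. R gives the same. Unpooled and arcsine calculations give 78.9% and 78.8%. Against 80%, the shortfall is 1.4 points, or 12 patients per arm (12/325 = 3.7%).

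**Step 3: missing outcomes.** The documents give no rate, so 5–20% is an assumption. As a complete-case approximation, treat each patient with a missing endpoint as contributing nothing and put the reduced n into the Step 2 formula:

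| Assumed missing | Evaluable per arm | Power |
|---|---|---|
| 0% | 325 | 78.6% |
| 5% | 308.75 | 76.5% |
| 10% | 292.5 | 74.2% |
| 15% | 276.25 | 71.8% |
| 20% | 260 | 69.2% |

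If half of the missing information were recovered (a further assumption), the effective losses would be 2.5, 5, 7.5 and 10%, and power would be 77.6, 76.5, 75.4 and 74.2%.

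**Step 4: the label.** Protocol 9.1 defines recanalization as a worsening on the Raymond Scale, assigns 73% of it to the control arm and 82% to the larger-coil arm, and calls the difference an improvement. The complements are 27% and 18%. The Background cites recurrence of about 10–20%, up to 33% in one study, which fits 27% and 18% and not 73% and 82%. SAP 6.5.2 uses the same figures as occlusion rates. The intended direction is therefore clear.

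**Step 5: which endpoint.** Correcting the direction does not make the two definitions equal. Under protocol 3.1, no change from the post-coiling appearance is a success. Under SAP 5.1, success is Raymond 1 or 2, and any considered angiogram above 2 is a failure. A patient who moves from Raymond 1 to 2 has recanalized under protocol 9.1 but is a success in the SAP. A patient left at Raymond 3 who stays there is unchanged under the protocol but a failure in the SAP. Neither document says which definition the 73% and 82% belong to.

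**The case against.** **The SAP says approximately, and 78.6% is approximately 80%.** This stands. A reader might infer that the SAP's calculation is wrong or that the trial is materially undersized even with complete data. The documents do not support that: the SAP's own claim reproduces to within two points, and 78.6% does not contradict its description of the power as adequate. The mismatch is with protocol 9.1's unqualified figure, and by itself it is small.

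**The attrition figures overstate the loss.** This stands in part. Under SAP 5.1 and 6.5.3, a patient with an earlier inadequate angiogram is already a failure, and deaths that are aneurysm-related or of unknown cause are scored as failures. The protocol's second analysis likewise counts death or morbidity that precludes angiography as an event. None of these patients is simply lost. The rest are imputed, with 3–6 month status in the model. But anyone inadequate at 3–6 months is already classified, so a patient being imputed has either an adequate early result or none. Among those with an adequate early scan, that variable cannot separate later failures from successes. Some information is kept, but not all of it.

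**No missing rate is documented.** This also stands. It would be wrong to assert that the trial will have some particular power in the low seventies. Only a range under stated assumptions is defensible.

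**The planned test is not a two-proportion test.** An unadjusted Wald test on the log risk ratio has 77.9% power by normal approximation, and 78.7% by exact enumeration. A reader might take 77.9% as the power of the planned analysis. It is not, because SAP 6.5.1 adjusts for rupture status and wide neck, and the documents give no covariate effects from which to compute that power.

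**Conclusion.** The point holds in two parts of unequal weight. The smaller is that 325 per arm gives 78.6% power with complete outcomes. That agrees with the SAP's approximate claim but not with the protocol's 80, for which 337 per arm are needed. The larger is that no allowance is made for missing or unreadable 12–18 month angiograms, although both documents anticipate missing follow-up imaging, so delivered power falls below 78.6% once endpoint information is lost. The extent depends on a rate the documents do not give: about 74% at 10% missing and 69% at 20% as a complete-case approximation, and higher to the extent that failure-scoring and imputation preserve information. All these figures take the 73% and 82% assumptions as given.

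The recanalization label in protocol 9.1 is a genuine contradiction. A reader might infer from it that larger coils are expected to do worse. Section 9.1's own reference to an improvement, the hypothesis in protocol 2.2 and SAP 6.5.2 all point the other way. The error is in the label, but the difference between the endpoint definitions behind it is real and is not settled by relabelling.

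**What to change.** No additional enrolment is proposed.

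1. In SAP 6.5.2 and protocol 9.1, state that 650 patients (325 per arm) give 78.6% power for 73% versus 82% at two-sided 0.05 with complete outcomes.
2. Add a power range for missing endpoints, labelled as a complete-case approximation under assumed rates, for example about 74% at 10% and 69% at 20%. Note that the rates are not estimates and that failure-scoring and imputation may reduce the loss.
3. In protocol 9.1, relabel 73% and 82% as rates of the favourable outcome.
4. Reconcile the Raymond-increase definition in protocol 9.1 with the Raymond 1 or 2 endpoint in SAP 5.1, and state which one the 73% and 82% assumptions refer to. Copying the SAP definition into 9.1 without checking where the rates came from would hide the difference.

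Items 1 to 3 cost only wording, and the stated power becomes less favourable. Item 4 needs the team to confirm the basis of the two rates. The SAP allows revisions before data lock.

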### 6.5.3 *Missing Primary Endpoint Data*

Patients without previous evidence of inadequate angiographic occlusion, either on the 3 to 6 month visit angiogram or on a clinically driven angiogram taken prior to study exit, that miss the 12 to 18 month angiogram, or whose 12 to 18 month angiogram is not readable by the core lab, will be missing the primary endpoint. Patients missing the primary endpoint who die prior to or during the 12 to 18 month visit window (up to 18 months post-randomization) and die with known cause of death related to their aneurysm or unknown cause of death will be considered treatment failures with inadequate occlusion. Patients missing the primary endpoint with a known cause of death unrelated to their aneurysm will be considered missing.

Patients with missing primary endpoint data will have their 12 to 18 month angiographic

occlusion status imputed via multiple imputation assuming that the data are missing at random. The imputation model will be stratified by randomization assignment and include age, sex, randomization strata for aneurysm status, randomization strata for wide neck status, aneurysm size, and angiographic occlusion status at the 3 to 6 month visit. Since this model includes a mixture of variables types (i.e. continuous and binary), a fully conditional specification method will be used (Berglund 2014).

The main feature of the imputation approach is the creation of a set of clinically reasonable imputations for angiographic occlusion for each patient with missing data. This will be accomplished using a set of repeated imputations created by predictive models based on the majority of participants with complete data. The imputation models will reflect uncertainty in the modeling process and inherent variability in patient outcomes, as reflected in the complete data. Thirty datasets will be imputed.

After the imputations are completed, all of the data (complete and imputed) will be combined and the analysis performed for each imputed-and-completed dataset. Rubin's method of multiple (i.e., repeated) imputation will be used to estimate treatment effect (Rubin 1986).

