### ***5.2 Intention to Treat***

From the moment of randomization, the patient will be included in the trial irrespective of whether they receive the assigned treatment regimen. Similarly, all enrolled patients will receive clinical follow-up and will be included in the final analysis.

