##### **Safety Population**

The safety population will consist of all randomized subjects who initiate endovascular coiling, grouped by their assignment at randomization regardless of whether or not they actually received the coil size to which they were assigned. The safety population will therefore be identical to the ITT population if all randomized patients receive attempted vascular coiling. The safety population will be used to present safety summaries and for the analysis of safety data.

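### A randomized aneurysm that is never treated and has no disqualifying angiogram is imputed from coiled aneurysms, although it is known not to be occluded

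*Combined protocol and SAP*

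**What the plan says.** **Who is analysed.** Protocol 5.2 states: "From the moment of randomization, the patient will be included in the trial irrespective of whether they receive the assigned treatment regimen". SAP section 4 defines the ITT set as everyone randomized, whatever treatment followed, and uses it for the primary endpoint. Randomization comes before embolization (Protocol 5.5 and the visit schedule in 6.1).

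**Non-treatment is foreseen.** Under Safety Population, SAP section 4 says: "The safety population will therefore be identical to the ITT population if all randomized patients receive attempted vascular coiling". A patient in whom coiling is never started leaves the safety set but stays in the ITT set.

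**Missed treatment has no rule.** SAP 6.3 has missed treatment in its title, but its text begins "Crossovers (patients who after randomization switch from the allocated treatment to the non-allocated" and deals only with changes between the two arms.

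**How a missing outcome arises.** SAP 5.1 makes any considered angiogram with a Raymond score above 2 a failure. SAP 6.5.3 applies to patients with no such earlier evidence: one with no imaging at the last visit, or one "whose 12 to 18 month angiogram is not readable by the core lab, will be missing the primary endpoint". Death from an aneurysm-related or unknown cause turns missing into failure. Everything else, including death from a known unrelated cause, is imputed under missing at random in thirty datasets. The model is run separately by arm on age, sex, the rupture and neck strata, aneurysm size and 3 to 6 month occlusion.

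**The concern.** Missing at random says that, given the model's covariates, the unseen outcome behaves like the seen ones. That fails for an aneurysm that received no occlusive treatment. Its status is not in doubt, and nothing in the model separates it from a coiled aneurysm of the same size and stratum. Following SAP 6.5.3 as written therefore gives a value known to be wrong; this is more than a missing detail.

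At stake is what ITT is meant to measure. If the assigned strategy is not carried out and the aneurysm stays open, the comparison should count that. Imputation replaces it with the result expected had coiling gone ahead. If non-treatment were more common in one arm, that arm would benefit.

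**Working it through.** **Inputs.** From SAP 6.5.2: control success 73%; "a 9% absolute improvement (to 82%) in the incidence of angiographic occlusion in patients receiving larger coils"; 325 per arm; "Approximately 80% power on a two-sided proportion test"; significance level 0.05. The share of randomized aneurysms never treated and without a graded angiogram is in neither document. It is an assumption here: *u*_L in the larger-coil arm and *u*_S in control.

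**1. The plan's own figure.** For a two-sided test of two proportions:

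- mean rate = (0.73 + 0.82)/2 = 0.775; null term √(2 × 0.775 × 0.225) = 0.5906
- alternative term √(0.73 × 0.27 + 0.82 × 0.18) = 0.5871
- power = Φ[(0.09 × √325 − 1.96 × 0.5906)/0.5871] = Φ(0.792) = 78.6%

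This agrees with the stated approximate 80%. Exactly 80% would need 337 per arm.

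**2. What the imputation assigns.** Within-arm logistic imputation was simulated with 300 replicates, 325 per arm, 10 never-coiled aneurysms per arm and 30 imputations. There was no treatment-received term, and 3 to 6 month status was left out because these aneurysms have none. Mean imputed success among the never-coiled was 72.8% with smaller coils and 81.3% with larger coils. In the simulation the covariates did not predict outcome, so this shows only that the arm's average rate is passed on. In the trial the value will follow observed rates and each patient's covariates.

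**3. Effect on the comparison.** With imputation the expected rates stay near 82% and 73%: difference 9.0 points, risk ratio 82/73 = 1.123. With untreated cases counted as failures:

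difference = 82(1 − *u*_L) − 73(1 − *u*_S)

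| *u*_L | *u*_S | Larger coils | Smaller coils | Difference | Risk ratio | Power at 325 per arm |
|---|---|---|---|---|---|---|
| 0 | 0 | 82.0% | 73.0% | 9.0 | 1.123 | 78.6% |
| 2% | 2% | 80.4% | 71.5% | 8.8 | 1.123 | 75.0% |
| 3% | 3% | 79.5% | 70.8% | 8.7 | 1.123 | 73.2% |
| 5% | 5% | 77.9% | 69.4% | 8.6 | 1.123 | 69.7% |
| 3% | 1% | 79.5% | 72.3% | 7.3 | 1.101 | 58.2% |
| 1% | 3% | 81.2% | 70.8% | 10.4 | 1.146 | 87.4% |

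- Equal shares: the shift is 9*u* points, so 0.45 at 5%. The factor (1 − *u*) cancels from the risk ratio, which is the SAP's primary effect measure.
- Unequal shares: imputation overstates the difference by 82*u*_L − 73*u*_S. At 3% and 1% this is 2.46 − 0.73 = 1.7 points. At 1% and 3% it is 0.82 − 2.19 = −1.4 points, an understatement.
- In numbers, 3% of 325 is about 10 aneurysms. Of these, about 8 (larger coils) or 7 (smaller coils) would be credited as occluded.

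**The case against.** The strongest reply is that existing rules already catch many of these cases. SAP 5.1 refers to the patient's angiograms without requiring that the aneurysm was coiled, and it times the endpoint from randomization. An untreated aneurysm that is imaged and graded above 2 is a failure and is not imputed. Some deaths before treatment are failures too. This stands, and it rules out the reading that every never-coiled aneurysm is credited with 73% to 82% success. It does not close the gap. The protocol's follow-up windows (5.1.3) run from coiling, so an uncoiled patient has no defined imaging window there. Neither document says how the core lab grades an uncoiled aneurysm, or whether images from an abandoned procedure count as clinically driven.

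A reader might also infer that the rule favours larger coils, because the operator knows the arm beforehand. The documents do not support that. Inclusion criterion 2 and Protocol 5.1.2 item 1 require that the aneurysm be treatable either way. Protocol 5.1.1 item 5 and 5.1.2 item 2 provide for a change of coil or device, with the patient kept in the study. Knowing the arm makes unequal non-treatment possible; no passage shows that it occurs or in which direction.

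Finally, one might want to fail every aneurysm in which no coil was left. That goes too far. Other devices are allowed for safety, and such a rule would override an observed Raymond 1 or 2 in an aneurysm closed by a device or a clip.

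The disposition table in SAP 6.4.1 will show how many received their assigned treatment, but it does not separate never-treated cases from crossovers.

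**Conclusion.** The point holds for a narrow group: randomized, given no occlusive treatment, with no angiogram graded above Raymond 2, and not dead of an aneurysm-related or unknown cause. For them SAP 6.5.3 imputes a result that cannot be right. The 73% and 82% are planning rates, so the credit is an expectation and not a fixed amount.

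The likely effect is small. Equal shares of up to 5% change the difference by under half a point and leave the risk ratio at 1.123. A material effect needs unequal shares, for which the documents give no evidence; the 1.7-point overstatement rests wholly on the assumed 3% and 1%. This is a cheap improvement, best settled before arm-level counts are seen so that the classification is not driven by the data.

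**What to change.** Add to SAP 6.5.3, with a cross-reference from 6.3:

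- A randomized aneurysm that received no occlusive treatment (no coil, other device or clip) by the end of follow-up, and that has no core-lab-graded follow-up angiogram, counts as inadequate occlusion in the primary ITT analysis and is not imputed.
- An aneurysm treated by another device or by clipping keeps its observed Raymond score.

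Add one sensitivity analysis of the primary endpoint in the safety population already defined (coiling initiated). That set still contains cases where coiling was started and abandoned, so it complements the rule and does not mirror it.

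The cost is a short SAP revision, which the SAP permits before data lock, and one extra run. Occlusion rates fall slightly in both arms and the expected absolute difference shrinks marginally. Power falls too: at an assumed 2% in each arm it is 75.0%, against 77.8% if those cases are simply left out (98% of 325 per arm at 73% and 82%).
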